Exclusion criteria. Decline to be randomized, unable to give consent or respond to questionnaires, history of colon surgery, active inflammatory bowel disease, lower gastrointestinal bleeding (except for occult blood or FIT positive in the context of colon cancer screening), therapeutic colonoscopy (e.g., hemostasis, removal of large polyp), proctosigmoidoscopy, bidirectional endoscopy, inadequate consumption of bowel preparation, known history of severe diverticulosis or diverticulitis, history of abdominal surgery previously requiring sedation for colonoscopy, current narcotic/anxiolytic medication use, prior unsuccessful experience with unsedated colonoscopy, emergent colonoscopy, evidence of colonic obstruction based on pre-colonoscopy clinical evaluation, current participation in other studies, medical condition that could increase the risk associated with colonoscopy (e.g., active cardiac or pulmonary disease or other serious disease), medical condition that would preclude a benefit from colonoscopic screening (e.g., cancer or any terminal illness), prosthetic heart valve, anticoagulant therapy, nonmedical problems (e.g., psychiatric disorders, excessive use of alcohol), need for special precautions in performing colonoscopy (e.g. antibiotic prophylaxis), and request of on demand sedation.

Primary outcome measure (for male and female subjects).

	_
Real time maximum insertion	_
pain (RTMIP) (unblinded) score	
(validation by correlation with	
recalled pain described below)	

Pain during insertion reported to the unblinded assisting nurse, visual analogue scale, VAS: 0=none, 10=most severe. The highest pain score will be tabulated for analysis. Timing of data collection will be at the discretion of the nurse to minimize bias by colonoscopist behavior.

Secondary outcome measures (for male and female subjects).

Proportion with no insertion pain Proportion report no pain during insertion of the colonoscope. Quality marker.

Insertion time	Time to cecum (clock display on monitor). Faster insertion is a quality marker
Proximal colon ADR	ADR from cecum to splenic flexure. Measure of high quality colonoscopy

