Primary outcome. Patient with insertion pain that cannot be brought to a tolerable level by colonoscopist implemented maneuvers will be considered failure of cecal intubation and the insertion will be discontinued. The pain level at the time of discontinuation will be noted for analysis.

Standardized validated instruments.

Proportion with no insertion pain, insertion time, proximal colon ADR (secondary outcomes in males) have been defined above; demographic data, co-morbidities, prior history and additional procedure based and patient level parameters will be analyzed as covariables (Tables 9 and 10).

Table 9: Demographic variables, co-morbidities and prior history				
Age	In years		Hemorrhoids	0=no, 1=yes
Gender	Male, female		Chronic pain treatments	0=no, 1=yes

Education	Elementary, high, college, graduate	Substance abuse	0=no, 1=yes
Ethnicity	White, Black, Hispanic, Asian, other	Prior abdominal surgery	0=no, 1=Yes (type)
BMI	Weight/height ²	Prior sedation colonoscopy	0=no, 1=yes
Indication	Screening, surveillance, diagnostic, pain	Prior unsedated colonoscopy	0=no, 1=yes

Table 10: Additional procedure based and patient level covariates				
Recalled maximum insertion pain	Maximum pain during insertion reported to a blinded observer after			
score (blinded data)	colonoscopy before discharge, VAS: 0=none, 10=most severe. Correlation with RTMIP.			
Overall ADR - entire colon	Proportion of patients with at least one adenoma of any size.			
Right colon ADR	ADR from cecum to hepatic flexure			
Adequacy of patient blinding	Patient guesses which method is used (<60% correct=adequate).			
Successful cecal intubation	0=no, 1=yes			
Successful cecal ilitubation	Abdominal pain prior to start of colonoscopy: 0, none to 3, severe (recorded			
Current abdominal discomfort	before examination)			
Loop reduction maneuvers	Number of times used, recorded by nurse assistant			
Position change	Start with left lateral, change as needed to supine, right lateral, prone.			
Abdominal compression	0=no, 1=Yes (sigmoid, transverse, hepatic, right side)			
Need to change technique	0=no, 1=yes (to air insufflation)			
Water volumes (insertion) Volume of water (infused and suctioned) upon arrival to the cecum, eq				
	volumes confirm appropriate application of water exchange			
Water volumes (total)	Volume of water (infused and suctioned) at the end of colonoscopy			
	Documented during withdrawal (4=excellent, no residual stool; 3=good, small			

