In both male and female Veterans, record will be kept of all these variables, however, to demonstrate comparability of the study and control groups. When the male and female data are combined, the sample size may reveal differences between WE and WECAC that are worth pursuing, thus providing pilot data for future studies (e.g. overall and segmental adenoma detection rates in scheduled unsedated subjects).

Statistical Analysis. Analysis will be performed based on assigned groups using STATA software (StataCorp 2013. Stata Statistical Software. College Station, TX: StataCorp LP). Descriptive statistics (frequencies, measures of central tendency and dispersion) will be used to evaluate the distribution of each variable. Data as mean (SD) or median (IQR) will be assessed by 2-samples independent samples tests (e.g. Student's t), Fisher exact test; relative risk tests and correlation analysis will be used to evaluate hypotheses. P<0.05 will be considered significant. Statistical assumptions required will be checked and appropriate data transformations or non-parametric test (e.g. Wilcoxon-Mann-Whitney *U test*,) will be used if assumptions are not met. Linear regression will be used to determine significant factor(s) that impact on the primary outcome. The analysis will use intention-to-treat principles, i.e., all randomized patients will be included in the analysis even if their colonoscopies were discontinued early (e.g., pain, poor preparation). The pain score at discontinuation will be used for the analysis for patients with early discontinuation.

Hypotheses Testing. There will be one-interim analysis and a final analysis for this study. The interim analysis will be conducted after 50% of subjects have been evaluated. This interim analysis will be for the primary analysis alone. The significance level for the interim analysis will be 0.0054 based on the standard O'Brien-Flemming rule. The study will be stopped if there is a significant result for the interim analysis. The final analysis will use a 0.0492 level of significance.

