- 8. Investigators may alter the WE technique (e.g., more frequent shortening maneuver) making it more difficult to detect a difference between techniques. Since the adjunct maneuvers are standard, investigators will be asked to use them consistently, and their use will be recorded. The RCT will be carried out by experienced colonoscopists with varying exposures to WE and WECAC, to assess the generalizability of the findings. The insertion technique for the water groups will be standardized by having the air pump turned off until the cecum is reached. Investigators will adhere to the details of both techniques described in the Methods section. There will be no limit on the water volume. Close attention will be paid to keep record of these variables to detect variations that may impact on interpretation of the results.
- 9. Differential dropout can result from patients being more likely to drop out of the trial if they have pain during the examination; resulting in more people dropping out of the control arm compared with the active treatment arm (presumably with less pain). They will be retained in the data analysis (intention-to-treat) and labeled treatment failures to avoid the differential dropout rate seriously biasing outcomes.
- 10. A different problem can occur in an intervention study if the subjects are not randomized to the treatment group they prefer: the subjects may drop out of the study before beginning treatment. In this study patients will be blinded to treatment assignment.
- 11. By the time evaluation of the WECAC is completed new technologies will have evolved to make WECAC obsolete. WE has been well-described and convincingly reduces RTMIP. The WECAC technique has been reported by us. Caps with other configuration (Daisy) are being reported. Endo Ring, G-Eye colonoscope, Endocuff and Daisy Caps have not been evaluated for their impact on colonoscopy insertion pain.

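### RTMIP is defined as the highest insertion pain score, but early stoppers are scored at the moment of discontinuation, which can understate the primary endpoint

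*SAP*

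**What the plan says.** Four places bear on the RTMIP value of a patient whose insertion is not completed.

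- Protocol, section (4)(b), primary outcome measure: RTMIP is pain on a 0-10 scale reported to the assisting nurse during insertion, and "The highest pain score will be tabulated for analysis".
- Protocol, section (4)(e), Primary outcome paragraph, on stops for pain: "Patient with insertion pain that cannot be brought to a tolerable level by colonoscopist implemented maneuvers will be considered failure of cecal intubation". Insertion then ends. The next sentence reads "The pain level at the time of discontinuation will be noted for analysis".
- SAP, Statistical Analysis: all randomized patients are analysed "even if their colonoscopies were discontinued early (e.g., pain, poor preparation"). The rule for them is "The pain score at discontinuation will be used for the analysis for patients with early discontinuation".
- SAP, Potential problems, item 9: of patients who drop out with pain, "They will be retained in the data analysis (intention-to-treat) and labeled treatment failures". The item expects pain to drive dropout, "resulting in more people dropping out of the control arm compared with the active treatment arm".

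The SAP's Primary hypothesis paragraph analyses RTMIP by a two-sample t-test, or by Mann-Whitney if the data are clearly non-normal. The Interim analysis paragraph applies the same analysis at 50% of subjects.

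**The concern.** The endpoint is a maximum over the insertion. The early-stopper rule takes a value at a single moment. Nothing in either document says that the score at discontinuation means the highest score up to that point, and the rule appears in both the protocol and the SAP, so it is hard to dismiss as a slip. Followed literally, it gives completers and stoppers different variables under one name.

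The gap is easiest to see for a stop unrelated to pain. A patient who reaches 7 at an earlier bend and stops for poor preparation while reporting 1 has an RTMIP of 7 under the protocol definition and 1 under the SAP rule. Protocol Table 10 has its own row for failures due to poor preparation, so such stops are foreseen.

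At stake is the recorded value of the primary endpoint in a small group of patients, at both the interim and the final analysis. Because stops may be unequal between arms, the error need not cancel. Item 9 adds a label without saying whether it affects the RTMIP score, which leaves room for a choice after the data are seen.

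**Working it through.** **1. The plan's own figure.** Inputs from the SAP, male sample size: difference 2.7 - 1.5 = 1.2, SD 2.2, two-sided alpha 0.0492, power 90%. The t-test calculation gives 71.9 per group, rounded up to the stated 72, and 144/0.9 = 160 to recruit. The figure reproduces, and the point does not change it.

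**2. Direction for one patient.** The score at discontinuation is one of the scores over which the maximum is taken. Hence score at stop ≤ maximum, and any error in that patient's RTMIP is downward.

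**3. Effect on the difference between arms.** Let f be the share stopping early in each arm and k the average of peak minus stop score, taken as the same in both arms. Then:

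change in (WE mean - WECAC mean) = -(f_WE - f_WECAC) × k

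The documents give no value for k. It is an assumption here; 0 is possible, and 2 to 4 points is used for illustration.

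**4. Rates from the documents.** Cecal intubation failure stands in for early stopping, which is itself an assumption.

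- Male pilot (SAP, male secondary outcome table): intubation 98% WE, 100% WECAC, so failures are 2% and 0%. Change: 0.02 × 2 = 0.04 to 0.02 × 4 = 0.08, that is 0.04/1.2 = 3% to 0.08/1.2 = 7% of the target. The observed difference becomes 1.16 to 1.12.
- Female pilot (SAP, female table): 100% in both arms, so the change is 0, on only 5 and 4 patients.
- Protocol Table 6: WE 97.6% and 96%, WECAC 96% and 96%. Failures are 2.4% and 4% against 4% and 4%. The gap in rates is 0, or 0.024 - 0.04 = -0.016. The change is then 0, or a widening of 0.016 × 2 = 0.03 to 0.016 × 4 = 0.06 points.

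**5. Power, males, 72 per group.** The standard error is 2.2 × √(2/72) = 0.367, and the critical value for alpha 0.0492 is 1.967. Power = Φ(difference/0.367 - 1.967), with the SD held at 2.2.

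| Failures WE / WECAC | k | Difference | Power |
|---|---|---|---|
| any | 0 | 1.20 | 90.4% |
| equal | any, same in both arms | 1.20 | 90.4% |
| 2% / 0% | 2 | 1.16 | 88.4% |
| 2% / 0% | 4 | 1.12 | 86.2% |
| 5.4% / 0% | 2 | 1.09 | 84.4% |
| 5.4% / 0% | 3 | 1.04 | 80.6% |

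The last two rows are a stress case. The 5.4% is the pain-failure rate reported with Protocol Table 4. It comes from a general unsedated series that left out poor preparation and obstruction, so it counts pain stops, for which k may be near zero. In females the same 5.4% / 0% with k = 2 moves 2.70 to 2.59 and power from 92.2% to 90.0% at 43 per group.

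**6. Opposite split.** If 5.4% stopped in WECAC only, the male difference would rise to 1.2 + 0.054 × 2 = 1.31 for k = 2.

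**The case against.** A reader might infer that the rule understates pain in the very patients who fared worst, and so biases the primary comparison. The documents do not support that.

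- The protocol ends insertion for pain only when the maneuvers have failed to make the pain tolerable. Such a patient stops while pain is still high, so the stop score is probably at or near the peak. That maneuvers come first does not show that pain had fallen.
- A sizeable shift needs both a real gap between peak and stop score and unequal stop rates. The gap is plausible mainly for stops unrelated to pain. For those the documents give no reason to expect the arms to differ: split-dose preparation is standardized for both arms, and inadequate consumption of the preparation is an exclusion. Multiplying a pain-stop rate by a gap typical of poor-preparation stops mixes two groups.
- If stops fall mainly in WE, as item 9 expects, lower WE scores shrink the difference. That is a loss of power and not a false-positive risk.
- Under the Mann-Whitney alternative, a stopper recorded a point or two below a high peak would still rank near the top, so the mean-shift arithmetic probably overstates the effect.
- The treatment-failure label can be read as describing retention under intention-to-treat, in line with the protocol's failed cecal intubation, and need not be a rival score.

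All of this stands, and it limits the size of the point. It does not remove the mismatch: the stated rule can record a value that is not the defined endpoint, and no passage equates the two.

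**Conclusion.** The point holds as an inconsistency in how the primary endpoint is scored. The rule can understate RTMIP in early stoppers, most clearly where the stop was not for pain or where pain had eased first. For pain stops the two scores will often be the same.

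The size is small on the trial's own pilot figures: 0.04 to 0.08 of 1.2 points in males for an assumed shortfall of 2 to 4 points, with power falling from 90.4% to between 88.4% and 86.2%. It is zero if the scores coincide, or if stop rates and shortfalls are the same in both arms. Table 6 would put it at zero or slightly reversed. These results assume that intubation failure stands in for early stopping, that the SD is unchanged and that the t-test is used. Neither the shortfall nor its split by arm can be derived from the documents, so a definite between-arm bias should not be claimed.

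Nor should item 9 be read as a contradictory scoring rule. What it lacks is a statement of whether "labeled treatment failures to avoid the differential dropout rate seriously biasing outcomes" has any bearing on the RTMIP score.

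**What to change.** In the SAP's Statistical Analysis paragraph, replace the early-discontinuation sentence with: *For patients with early discontinuation, RTMIP is the highest pain score recorded from the start of insertion up to and including discontinuation.* Align the Primary outcome paragraph in Protocol section (4)(e).

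Add that this value is still truncated, since pain over the rest of the insertion is not observed. In SAP Potential problems, item 9, state that the treatment-failure label is descriptive and does not replace the RTMIP score. A sensitivity analysis placing pain-related stops at the worst rank is optional and would address the truncation.

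The cost is one SAP sentence, a matching protocol sentence and a short clarification. The highest score is already to be tabulated, so no new data are needed and the sample size does not change. If peak and stop scores always coincide, the results are unaffected.

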Primary hypothesis. Real-time maximum insertion pain (RTMIP) is significantly lower in the patients examined by the WECAC technique compared with the WE technique. The analysis will compare 2 groups (WECAC vs. WE) with a two sample t-test. If the data show substantial non-normality (as in a prior dataset with WE (5)); we will compare the groups with a Mann-Whitney *U* test; P<0.0492 considered significant. Secondary analysis of the primary outcome will utilize mixed effects regression models to evaluate the effects of potential covariates/confounds described in Tables 9 and 10. First, we will assess the effect of each individual covariate in regression models including the effect for group assignment and gender (stratification factor in the randomization), as well as the covariate by group interaction. Next, we will construct a multiple regression model with the set of covariates found to be significant (either as a main effect or an interaction effect) in an overall regression model along with group assignment.

Dependent Variables	Variable Type	Analysis method
Primary Outcome		
RTMIP (0=none,	Continuous	2 sample Student t test. However, if distribution of the data is skewed as
10=most severe)	Continuous	seen in an earlier study (5), the Mann-Whitney U test will be used.

We have updated the analytic plan to include multi-level random effects (hierarchical model) for study site and provider within site. We will include two levels of random effects in this model: 1. random effects for study site, 2. random effects for provider which will be nested within sites.

Secondary hypotheses. WECAC produces significantly higher quality colonoscopy outcomes. For example, when WE alone and WECAC are compared, the proportion completing colonoscopy with no pain, insertion time, and ADR in the proximal colon will be significantly different. For continuous secondary outcomes (e.g. insertion time), we will use a similar analysis strategy as that used for the primary outcome. For dichotomous secondary outcomes (e.g., no pain, proximal colon ADR) we will use Chi-square tests to compare the outcomes between the groups. Generalized logistic models will be used to adjust for covariates, gender and study site for these outcomes.

Dependent Variables	Variable Type	Analysis method
Insertion time	Continuous	Student t test
No insertion pain (yes, no); proximal colon adenoma detection (yes, no)	Binary	Chi square

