chronic pain treatment, substance abuse, prior abdominal surgery, prior colonoscopy with or without sedation, current abdominal discomfort, expectation on day of colonoscopy, patient reported pain tolerance and subjective anxiety, objective anxiety assessed by colonoscopist, and reason for choice of no sedation. Procedure-related factors include technique of insertion, use of loop reduction maneuvers by the colonoscopist, change of patient position, application of abdominal compression by the assistant and insertion time, and length of colonoscope needed to reach the cecum. Examples: patients are more likely to report higher RTMIP amongst those with younger age, longer duration of insertion, lower expectation of painless insertion, female gender, low BMI, more frequent need for position change or abdominal compression. More patients will report lower RTMIP if there is low patient anxiety, good expectation of today's examination, no

prior abdominal surgery, colonoscopist use loop reduction maneuvers. The analysis of the exploratory outcomes will follow the same structure as the primary and secondary outcomes. To control for the multiplicity of exploratory outcomes we use the false-discovery rate (FDR) of Benjamini and Hochberg (67) rather than the traditional Bonferroni adjustment. The FDR assesses estimates the proportion of significant findings that are false positive results. The FDR method is less conservative and better preserves our ability to detect differences between groups.

Interim analysis. After 50% of subjects complete the protocol and data collection we will perform an inferential analysis of the primary endpoint as described in the statistical methods section. The only difference between the interim analysis of the primary endpoint and the final analysis will be the level of significance of the tests. If there is a significant treatment effect, this would communicated to the study Data and Safety Monitoring Board (DSMB) to consider early termination for efficacy.

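### The interim and final levels 0.0054 and 0.0492 give an overall type I error of 0.0513, not 0.05, and the SAP has two rules for what an interim crossing does

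*SAP*

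**What the plan says.** The SAP paragraph on hypothesis testing plans two analyses of the primary outcome, real-time maximum insertion pain (RTMIP). On timing: "The interim analysis will be conducted after 50% of subjects have been evaluated". On levels: "The significance level for the interim analysis will be 0.0054 based on the standard O'Brien-Flemming rule", and "The final analysis will use a 0.0492 level of significance". The male and female sample-size paragraphs use the same 0.0492 and describe it as adjusted for an O'Brien-Fleming look at 50%. The primary-hypothesis paragraph repeats it: "P<0.0492 considered significant". No overall level for the two looks is stated. The nearest statement is the general line under Statistical Analysis, "P<0.05 will be considered significant".

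Two places say what follows an interim crossing. Under Hypotheses Testing: "The study will be stopped if there is a significant result for the interim analysis". Under Interim analysis, the result is passed on, in the words "DSMB) to consider early termination for efficacy".

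The Interim analysis paragraph also ties the interim to the final test: "The only difference between the interim analysis of the primary endpoint and the final analysis will be the level of significance of the tests". The final test is itself described in two ways. The protocol's primary hypothesis claims lower pain in men and in women, and the SAP sizes each gender separately at 90% power. The SAP's primary-hypothesis paragraph describes a single comparison of the two arms.

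**The concern.** The two levels are the thresholds on which success is declared, and the SAP attributes the interim level to the standard O'Brien-Fleming rule. If the pair does not hold the intended error rate, a stated decision threshold is wrong.

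The stop rule matters more in practice. The same interim p-value would end the trial under one paragraph and only open a discussion under the other.

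Because the interim inherits the final test, it also inherits the pooled-or-by-gender question. It is therefore unclear which result triggers the rule, and nothing says what happens if one gender crosses and the other does not.

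**Working it through.** **Inputs from the documents.** Interim level 0.0054, final level 0.0492, one look at 50%, two-sided two-sample t-test. Men: difference 1.2, SD 2.2, 72 per group. Women: difference 2.7, SD 3.7 (rounded to 0.7 SD), 43 per group. 90% evaluable.

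**The plan's own sample sizes.** By exact noncentral t at 0.0492 with 90% power, men need 72 per group at d = 1.2/2.2. Women need 41 at d = 2.7/3.7 and 45 at d = 0.70, either side of the stated 43. Dividing by 0.9: 144/0.9 = 160, and 86/0.9 = 95.6, rounded up to 96. The sizing is sound; only the levels are at issue.

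**Overall error of the stated pair.** The two-sided critical values are z1 = 2.7822 and z2 = 1.9669. The correlation between looks is √0.5. Overall error = 1 − P(|Z1| < 2.7822 and |Z2| < 1.9669) = 0.0513.

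The ratio z1/z2 is 1.4145, almost exactly √2, so the pair has the O'Brien-Fleming shape. Its constant is 1.967, whereas 5% requires 1.9774.

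| Interim | Final | Overall error | Basis |
|---|---|---|---|
| 0.0054 | 0.0492 | 0.0513 | as written |
| 0.0052 | 0.0480 | 0.0500 | O'Brien-Fleming, 5% |
| 0.0054 | 0.0479 | 0.0500 | interim level kept |
| 0.0026 | 0.0492 | 0.0500 | final level kept |
| 0.0031 | 0.0490 | 0.0500 | O'Brien-Fleming-type spending |

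Reading 50% as 128 (half of 256 recruited) out of 230 evaluable gives 0.0509. Reading it as 115 (half of 230) out of 256 gives 0.0516. Halving the levels for a one-sided test gives 0.0256 against 0.025. Simulated t-tests at 44, 72 and 116 per group gave 0.0520, 0.0512 and 0.0512. No variant tried brings the pair back to 5%.

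**Power if the sample sizes are kept.**

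| | At 0.0492 | At 0.0480 |
|---|---|---|
| Men, n = 72, d = 1.2/2.2 | 90.0% | 89.8% |
| Women, n = 43, d = 0.70 | 89.3% | 89.1% |
| Women, n = 43, d = 2.7/3.7 | 91.6% | 91.4% |

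**How often the stop rule would be used, pooled look.** Half of 72 + 43 = 115 per arm is about 58 per arm. The gender mix at that point is an assumption. The protocol's recruitment table (1 to 2 men per woman) spans 29/29 to 39/19 men/women per arm; the planned 72:43 ratio gives 36/22. Scores were simulated as normal with the pilot means, using an unadjusted t-test at 0.0054. Ranges cover three ways of setting the pilot SDs.

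| Men/women per arm | Crosses 0.0054 | Both genders at p < 0.0492, given crossing |
|---|---|---|
| 39/19 | 53–58% | 67–69% |
| 36/22 | 54–60% | 68–70% |
| 29/29 | 59–66% | 63–64% |

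A more male-heavy 44/14, which has no source in the documents, gives 51–56% and 58–61%. The last column is a yardstick for the protocol's claim in both genders, not a test in the SAP. If the female difference is halved to 1.35, crossing at 36/22 falls to about 19%, with both genders at 0.0492 in about 60% of those.

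**By-gender look.** With 36 men and 21 or 22 women per arm at 0.0054, exact t power is about 30% for men and 27–32% for women. Treating the genders as independent, exactly one crosses in about 41–43% of trials and both in 8–9%.

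**The case against.** The excess is 0.13 percentage points. Only a final p between 0.0480 and 0.0492, or an interim p between 0.0052 and 0.0054, would change a conclusion. The 5% target is inferred. The figure 0.0513 also counts an interim crossing as a rejection; if the trial continued and only the final test counted, the error would be 0.0492. All of this is correct. But neither stop-rule paragraph says that a crossing is to be disregarded, and describing 0.0492 as adjusted makes sense only against a 5% total.

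The Interim analysis paragraph can be read as the procedure for carrying out the rule under Hypotheses Testing. That reading is possible, but the text does not state it, and a result that must stop the study differs from one the board weighs.

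The simulation is the softest part. Normal scores on a 0–10 scale put about 24% of the WECAC men below 0 and about 14% of the WE women above 10, while the SAP expects skew and allows a Mann-Whitney test. Half-size subgroups will often miss 0.0492, so that column alone does not show a defect in the rule. The pooled-or-by-gender question also reaches beyond the interim. These limits stand, but the corrections to the levels and the stop rule do not depend on the simulation.

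**Conclusion.** The concern holds. If 5% two-sided is the intended total and an interim crossing counts as a rejection, the stated pair gives 0.0513 (0.0509 to 0.0516 over the readings of 50%). It matches neither the standard O'Brien-Fleming levels nor the spending-function version. The numerical effect is small.

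The two stop-rule statements conflict, and nothing else in the documents reconciles them. Under a pooled look with the plan's pilot effects, a crossing is more likely than not. With gender mixes the documents support, about 30% to 37% of crossings would come without both genders at 0.0492; the unsourced 44/14 mix raises the upper end to about 42%. Under a by-gender look, a crossing would usually involve one gender only, and the plan does not provide for that. These frequencies rest on an assumed gender mix and on a female effect from nine patients.

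**What to change.** 1. Replace the pair by 0.0052 and 0.0480, or keep 0.0054 with a final level of 0.0479, wherever the levels appear: both sample-size paragraphs, Hypotheses Testing and Primary hypothesis. State the overall two-sided level the pair is meant to hold.
2. Keep 72 men and 43 women per group and restate the power at the new final level. Raising men to 73 per group would restore 90%, but 146/0.9 = 162.2 exceeds the planned 160, so it is not proposed.
3. Reconcile Hypotheses Testing and Interim analysis into one rule that says whether a crossing is binding or is for the monitoring board to consider.
4. Settle whether the primary analysis is pooled or by gender, apply the same choice to the interim test and to its 50% point, and state what follows if only one gender crosses.

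The cost is SAP wording. Power changes by about 0.2 percentage points, and the targets of 160, 96 and 256 are unchanged.
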